Once the RP2D is determined, Phase II will begin with 2 expansion cohorts in 2 specified tumor types. The specified tumor types will be selected based on emerging data from this study and other ongoing studies. These data may include clinical data with avelumab or with other immune checkpoint inhibitors, or preclinical data providing additional rationale for a specific tumor type. Each expansion cohort will follow Simon's Optimal Two-stage Design. If there are 2 or more subjects with confirmed objective responses within the first 23 subjects treated at the RP2D, then an additional 33 subjects will be enrolled and treated at that dose level. If there are 1 or no subjects with confirmed objective responses in the first 23 subjects treated at the RP2D within a minimum follow-up of 16 weeks, then the cohort will be closed for further enrollment.

The study is aimed at defining a single RP2D in the age group 0 to < 18 years. However, if at any time during the study, data suggest a difference in tolerability by age, this will be discussed with the Safety Monitoring Committee (SMC). The following rules will be used:

- The first 3 subjects in the initial cohort will be 1 to < 18 years of age.
- Subsequent cohorts may be open to subjects 0 to < 18 years of age, or a narrower age range, based on emerging data, as agreed by the SMC.

Avelumab will be administered every 2 weeks until confirmed progression, death, unacceptable toxicity, or any criterion for withdrawal occurs. A cycle is defined as 2 weeks. In Phase I, the DLT observation period is defined as a 28-day period (2 cycles) beginning with the first avelumab administration. Each subject will be followed for 12 months after his/her end of treatment.

Baseline imaging will be performed within 28 days prior to registration and Cycle 1 Day 1 treatment in order to establish Baseline disease status of target and nontarget lesions according to RECIST 1.1. Acceptable modalities include CT scans (neck, chest, abdomen, and pelvis as

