- y. Tumor assessments post-Baseline: Tumor evaluation has a time window of 5 days prior to dosing (-5 days) and  $\pm 5$  days after the EOT Visit. CT or MRI scans will be performed every 4 treatment cycles (every 8 weeks) for the first 24 weeks, then every 12 weeks thereafter. If bone metastases were present at Baseline, or if new bone metastases are suspected, bone scintigraphy or  $^{18}\text{F}$ FDG-PET/CT will be repeated every 8 weeks for the first 24 weeks, then every 12 weeks thereafter. Bone imaging is also required at the time of CR confirmation for subjects who had bone metastases at Baseline. If PR, CR, or PD is observed according to RECIST 1.1, a confirmation CT or MRI should be performed, preferably at the regularly scheduled 8-week assessment but no sooner than 4 weeks after the first documentation of response or confirmed disease progression. Tumor assessment should be repeated at the EOT Visit if more than 4 weeks have passed since the last evaluation.
- z. Registration prior to dosing: Registration of subjects will proceed through the use of an interactive response technology system.
- aa. Pretreatment: Premedication with an antihistamine (H1 receptor blocker such as diphenhydramine) and with paracetamol (acetaminophen) approximately 30 to 60 minutes prior to the first 4 doses of avelumab is mandatory. Premedication can be administered for subsequent avelumab doses based upon clinical judgment and presence/severity of prior infusion reaction. This regimen may be modified based on local treatment standards and guidelines as appropriate provided it does not include systemic corticosteroids.
- bb. Avelumab administration: Avelumab will be given as a 1-hour infusion every 2 weeks (14 days). The biweekly, 14-day treatment schedule should be strictly adhered to, returning to the target date even if the previous visit was off schedule.

**Table 2** Schedule of Assessments – Pharmacokinetic and Antidrug Antibody Sampling

	Treatment Period (-3/+1 days) 1 Cycle = 14 Days									Follow-up Visits	
	Cycle 1 (Week 1)	Cycle 2 (Week 3)	Cycle 3 (Week 5)	Cycle 5 (Week 9)	Cycle 7 (Week 13)	Cycle 8 (Week 15)	Cycle 13 (Week 25)	Cycle 19 (Week 37)	Cycle 25 (Week 49) and Every 6 Cycles Thereafter	EOT/ Withdrawal Visit (Within 7 Days of Decision to Discontinue)	30-Day Safety Follow- up (± 5 Days)

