Tumor evaluation (see Section 7.3) will be performed every 8 weeks starting at Cycle 5 for the first 24 weeks, then every 12 weeks until the end of treatment or withdrawal from the study, and at the End of Treatment/Withdrawal Visit if more than 4 weeks has passed since the last evaluation.

Subjects will receive avelumab by iv infusion following pretreatment with an antihistamine (H1 receptor blocker such as diphenhydramine) and acetaminophen (paracetamol; oral or iv), approximately 30 to 60 minutes prior to each dose, once every 2 weeks for the first 4 infusions (see Section 5.1.2).

Assessments to be performed during the treatment period are presented in [Table 1](#) and [Table 2](#).

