Subjects who start treatment and discontinue from the study on the same day may have two different sets of data collected on study day 1 (one during study and one in the End of Treatment (EOT) visit). Data reported at the EOT visit are not eligible for baseline selection.

If a scheduled pre-dose measurement actually occurred post-dose, then the corresponding measurement will be treated and analyzed similar to an unscheduled post-dose measurement.

Baseline for HR and QT/QTc assessments will be derived from the visit where both HR and QT are not missing. QTcF will be derived based on HR and QT.

Definition of study day:

Study day is defined relative to the date of start of treatment. Study day 1 defines the day of first administration with avelumab, the day before is defined as study day -1 (no study day 0 is defined).

Definition of on-treatment period:

The on-treatment period is defined as the time from the first dose of study treatment through minimum (30 days + last dose of study treatment, start day of new anti-cancer drug therapy - 1 day).

The date of new anti-cancer drug therapy after start date is derived as outlined in Section 12.1.

Definition of duration:

Duration will be calculated by the difference of start and stop date + 1 (e.g. survival time (days) = date of death - date of first dose of study drug + 1).

The time since an event (e.g. time since first diagnosis) will be calculated as reference date minus date of event.

Standard derivations and reporting conventions:

The following conversion factors will be used to convert days into months or years:

1 week = 7 days, 1 month = 30.4375 days, 1 year = 365.25 days.

Demographic and physical measurements:

- Age [years]:
 - (date of given informed consent - date of birth + 1) / 365.25
 - In case only year and month of birth are given: Age [years]: (year/month of given informed consent - year/month of birth) / 12
 - In case only year of birth is given: Age [years]: (year of given informed consent - year of birth)

The integer part of the calculated age will be used for reporting purposes.

- BMI (kg/m^2) = weight (kg)/[height (m)]².
- BSA (m^2) = ([height (cm) × weight (kg)] / 3600)^{0.5} (1)

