14.4 Progression Free Survival per RECIST v1.1 (Secondary Endpoint)

The PFS time, according to the RECIST 1.1, is defined as the time from the start date of study treatment until the first documentation of PD or death due to any cause, whichever occurs first. PFS data will be censored on the date of the last adequate tumor assessment for subjects who do not have an event (PD or death), for subjects who start a new anti-cancer therapy prior to an event or for subjects with an event after two or more missing tumor assessments. Subjects who do not have a baseline tumor assessment or who do not have any post-baseline tumor assessments will be censored on the start date of study treatment unless death occurred on or before the time of the second planned tumor assessment, in which case the death will be considered an event.

PFS time (in weeks) is defined as:

$$(\text{date of PD or death} - \text{date of the first dose of study treatment} + 1) / 7 \text{ (weeks)}.$$

Specific censoring rules are defined in Table 2.

Table 2 Outcome and event dates for PFS and DOR analyses

Scenario	Date of event/censoring	Outcome
No baseline assessment	Start date	Censored ^a
PD or death ≤ 12 weeks after last tumor assessment or ≤ 12 weeks after start date	Date of PD or death	Event
PD or death > 12 weeks after the last tumor assessment	Date of last adequate tumor assessment ^b documenting no PD before new anti-cancer therapy is given or missed assessments	Censored
No PD	Date of last adequate tumor assessment ^b documenting no PD before new anti-cancer therapy is given or missed assessments	Censored
Treatment discontinuation due to 'Disease progression' without documented progression	Not applicable	Information is ignored. Outcome is derived based on documented progression only.
New anti-cancer therapy given	Date of last adequate tumor assessment ^b documenting no PD before new anti-cancer therapy is given or missed assessments	Censored

^a However if the subject dies ≤12 weeks after start date the death is an event with date on death date

^b If there are no adequate post-baseline assessments prior to the PD or death, then the time without adequate assessment should be measured from the date of first dose of study treatment; if the criteria were met the censoring will be on the date of first dose of study treatment

Censoring reasons will be listed according to the categories in Table 3 following the hierarchy shown.

Table 3 PFS censoring reasons and hierarchy

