Hierarchy	Condition	Censoring Reason
1	No baseline assessment	No baseline assessment
2	Start of new anti-cancer therapy before event.	Start of new anti-cancer therapy
3	Event more than 12 weeks after last adequate post-baseline tumor assessment	Event after missing assessments ^a
4	No event and [withdrawal of consent date ≥ date of first dose of study treatment OR End of study (EOS) = Subject refused further FU]	Withdrawal of consent
5	No event and lost to follow-up in any disposition page	Lost to follow-up
6	No event and [EOS present OR disposition page for any EPOCH after screening says patient will not continue into any subsequent phase of the study] and no adequate post-baseline tumor assessment	No adequate post-baseline tumor assessment
7	No event and none of the conditions in the prior hierarchy are met	Ongoing without an event

^a more than 12 weeks after last adequate tumor assessment.

Kaplan-Meier estimates (product-limit estimates) will be presented with a summary of associated statistics including the median survival time with two-sided 95% CIs. In particular, the

progression-free survival rate at 4, 8, 12, and 24 weeks will be estimated with corresponding two-sided 95% CIs. The CIs for the median will be calculated according to Brookmeyer and Crowley (4) and the CIs for the survival function estimates at the time points defined above will be derived using the log-log transformation according to Kalbfleisch and Prentice (5) (confype=loglog default option in SAS Proc LIFETEST) with back transformation to a CI on the untransformed scale. The estimate of the standard error will be computed using Greenwood's formula.

Frequency (number and percentage) of subjects with an event (progressive disease or death) will be presented.

A listing including subject ID, dose level, age, first and last dosing date, date of event (PD or death), the PFS time or censoring time, and the reasons for censoring will be provided.

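### The 8- and 24-week PFS rates are read one day before the nominal scan days, so they depend partly on which day in the window the scan was booked

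*SAP*

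**What the plan says.** SAP 14.4 defines PFS in weeks as event date minus first-dose date, plus one, divided by 7. From the Kaplan-Meier curve, the "progression-free survival rate at 4, 8, 12, and 24 weeks will be estimated", with two-sided 95% confidence intervals. SAP Section 9 fixes the time scale: "Study day 1 defines the day of first administration with avelumab" and "1 week = 7 days, 1 month = 30.4375 days, 1 year = 365.25 days". Its tumor-assessment rules date an evaluation by the actual scan, taking the earliest when there are several. Nothing maps scans to nominal visits.

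In the protocol, "A cycle is defined as 2 weeks" (Synopsis, Methodology). Section 7.1.2 says tumor evaluation "will be performed every 8 weeks starting at Cycle 5 for the first 24 weeks, then every 12 weeks", and footnote y to Table 1 says "CT or MRI scans will be performed every 4 treatment cycles (every 8 weeks) for the first 24 weeks". Table 1 prints Cycle 5 as Week 9, Day 57, and Table 2 prints Cycle 13 as Week 25. The scan window is one-sided: "Tumor evaluation has a time window of 5 days prior to dosing (-5 days"). The visit window is 3 days before to 1 day after the scheduled day (Table 1, first footnote).

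**The concern.** A landmark rate for a scan-based endpoint should be read where all scans of a given round fall on the same side of it. Here the 8- and 24-week reads cut through the scan windows. Two children with the same disease course, both found to have progressed at the first scan, can be counted differently because one was scanned on Day 56 and the other on Day 57.

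At stake is the meaning of two specified rates. They are planned for the clinical study report, and SAP Section 4 foresees use of the planned analyses in submissions or manuscripts. The confidence interval reflects sampling error, not booking day. If no event falls by Day 56 the estimate is 100%, and the planned log-log interval is undefined there.

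**Working it through.** **Scan days.** Day = 1 + (cycle - 1) x 14.
- Cycle 5: 1 + 4 x 14 = Day 57, which reproduces the day printed in Table 1.
- Cycle 9: 1 + 8 x 14 = Day 113.
- Cycle 13: 1 + 12 x 14 = Day 169. This day is not printed, but it agrees with Week 25 in Table 2. It assumes that the 8-weekly scans include the one at 24 weeks.

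**Landmarks.** PFS weeks = study day / 7, because of the +1. So 8 weeks = Day 56 and 24 weeks = Day 168.

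**Which side each scan day falls.** Kaplan-Meier counts events at or before the landmark.

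| Scan day | PFS (weeks) | Status at landmark |
|---|---|---|
| 52 to 56 | 7.43 to 8.00 | event by 8 weeks |
| 57 | 8.14 | progression-free at 8 weeks |
| 58 (visit +1 day) | 8.29 | progression-free at 8 weeks |
| 164 to 168 | 23.43 to 24.00 | event by 24 weeks |
| 169 | 24.14 | progression-free at 24 weeks |
| 170 (visit +1 day) | 24.29 | progression-free at 24 weeks |

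**The 12-week rate.** Twelve weeks is Day 84. The latest in-window first scan is Day 58, and the earliest in-window second scan is 113 - 3 - 5 = Day 105. Every in-window first-scan progression is therefore counted by 12 weeks, whatever the booking day.

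**Worked example.** Assume 12 subjects, 6 with progression at the first scan and no earlier events. The 8-week rate is:
- 6/12 = 50% if all six are scanned on Days 52-56;
- 7/12 = 58.3% if they are spread one per day over Days 52-57;
- 100% if all six are scanned on Day 57.

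Read at 9 weeks, it is 50% in each case. One subject moves the rate by 1/12 = 8.3 points at N=12 and 1/36 = 2.8 points at N=36, the limits of the planned Phase I size (protocol 5.1.1).

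**Size in general.** Shift = P(progression at first scan) x fraction of scans on Day 57 or later. The documents give neither input. Taking 40% and 60% for the first:

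| Assumption on scan days | Fraction late | Shift at 40% | Shift at 60% |
|---|---|---|---|
| Dosing uniform over Days 54-58, scan 0 to 5 days before | 3/30 = 10% | 4 points | 6 points |
| Dosing on Day 57, scan uniform over Days 52-57 | 1/6 | 7 points | 10 points |
| Half of scans on Day 57 or later | 1/2 | 20 points | 30 points |

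In the first row there are 5 x 6 = 30 combinations. Three are late: one with dosing on Day 57 and two with dosing on Day 58.

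The 24-week mechanism is the same. Its size in points also depends on how many subjects remain at risk, which the documents do not indicate.

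**The case against.** The case for leaving the text alone has several sound parts.

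- The 12-week rate, in the same sentence of the SAP, already gives a first-scan read that does not depend on booking day. This stands.
- With dosing on Day 57, five of the six permitted scan days count as events by week 8. The visit window reaches further back (3 days) than forward (1 day), and the SAP takes the earliest date of a multi-day evaluation. This stands. A reader might infer that progression found on schedule is generally counted as progression-free; the documents support that only for the nominal day and for scans tied to a late visit.
- PFS is defined by first documentation of progression, so a Day 57 progression is correctly undocumented on Day 56. This also stands. It is tempting to call the 8-week rate biased, but the defect is sensitivity to scan timing, not a departure from the SAP's own definition.
- A reader might suppose a rapidly progressing population in which most events surface at the first scan. The documents do not say so: exclusion criterion 19 bars rapidly progressive disease, and inclusion criterion 12 requires an expected survival of at least 3 months. The 40% and 60% inputs are assumptions only.
- The 4-week read precedes every scheduled scan, which might suggest dropping it. But deaths and end-of-treatment or unscheduled scans can produce events by then, so keeping it is reasonable.
- No decision rests on these rates. The SAP's modification history says Phase II data will not be analyzed, and the Kaplan-Meier estimates, the median and a listing of individual PFS times remain.

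These points limit the size and severity. They do not remove the misalignment, since nothing in the SAP maps scans to nominal visits.

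**Conclusion.** The misalignment is certain on the documents' own arithmetic for the first scan. For the third it rests on the natural reading that puts a scan at Cycle 13. Two of the four planned PFS rates depend partly on the day of the scan within its window; the 4- and 12-week reads do not have this problem. The plausible effect on the 8-week rate runs from about 4 points to 30 points, depending on two unstated inputs: the share progressing at the first scan and the share scanned on Day 57 or later. The low end follows if both windows are used evenly, and the high end needs half the scans on or after Day 57. Larger shifts would need most scans to be that late, which the documents give no reason to expect. Severity is low, because the endpoint is descriptive and no conclusion or rule turns on these rates.

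**What to change.** In SAP 14.4, replace the 8- and 24-week reads with 9 and 25 weeks. These are Days 63 and 175, beyond the latest in-window scans on Day 58 (8.29 weeks) and Day 170 (24.29 weeks). Keep the 4- and 12-week reads, the Kaplan-Meier curve and the median as planned.

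Removing the +1 from the formula would not be enough. Days 57 and 169 would become exactly 8.0 and 24.0 weeks and be counted, but Days 58 and 170 would still be missed, and the formula would depart from the duration convention in SAP Section 9. There is a precedent for a window allowance in SAP 14.5, where the loss-to-follow-up limit for overall survival adds a 1-week window to the 12-week interval.

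The cost is one sentence in the SAP and one option in the program. The downside is that 9 and 25 weeks are less conventional labels.

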14.5 Overall Survival (Secondary Endpoint)

Overall survival (OS) time is defined as the time from date of first dose of study drug to the date of death due to any cause. Subjects last known to be alive will be censored at date of last contact.

$$\text{OS (months)} = [\text{date of death or censoring} - \text{start date} + 1] / 30.4375$$

The date of last contact will be determined as specified in section 9.

Censoring reasons are as follows:

- Alive
- Withdrawal of consent
- Lost to follow-up

Lost to follow-up will include subjects that the investigator states were lost to follow-up prior to the analysis cut-off as well as subjects with a last contact date > 13 weeks prior to the analysis cut-off date. (13 weeks is based on the assessment schedule of every 12 weeks for survival follow-up interval + 1 week window.)

Analysis of OS will be analogous to the analysis of PFS, with Kaplan-Meier estimates of the survival rate produced for 2, 4, 6, 8, 10, and 12 months after treatment start.

A listing including subject ID, dose level, age, PD-L1 expression status, tumor type, sex, race, first and last dosing date, the overall survival time or censoring time, and the event or censoring description will be provided.

CCI

CCI

14.7 Tumor Shrinkage

Tumor shrinkage will be summarized as the percent change from baseline in target lesions (sum of longest diameter for non-nodal lesion and short axis for nodal lesion) per time point. It will be derived as:

- $[(\text{Sum of target lesions at week XX} - \text{sum of target lesions at baseline}) / \text{sum of target lesions at baseline}] \times 100$

The maximum reduction in target lesions from baseline will be derived across all the post-baseline assessments until documented disease progression, excluding assessments after start of subsequent anticancer therapy, as:

- Minimum of $[(\text{sum of target lesions at week XX} - \text{sum of target lesions at baseline}) / \text{sum of target lesions at baseline}] \times 100$

A waterfall plot of maximum percent reduction in the sum of longest diameter for non-nodal lesions and short axis for nodal lesions from baseline will be created overall with dose level indicated by varying colors. These plots will display the best percentage change from baseline in the sum of the diameter of all target lesions for each subject with measurable disease at baseline and at least one valid post-baseline assessment. In addition, the percent change from baseline for

sum of diameters will be displayed against time (weeks) in a line/spider plot. The lines of the plot will be color coded according to dose level. Markers for end of treatment, new lesion, non-target PD, death, and start subsequent anti-cancer treatment will be included in the plot.

15 Safety Analyses

The subsections in this section include specifications for summarizing safety endpoints that are common across clinical trials such as adverse events, laboratory tests and vital signs.

All safety analyses are performed using the SAF unless otherwise stated.

15.1 Dose-Limiting Toxicities (Primary Endpoint - Phase I)

Analysis Set: DLT

The primary endpoint of the Phase 1 study is the incidence of DLTs occurring during the DLT evaluation period (28-day period, first 2 cycles of treatment) in order to determine the RP2D. DLTs are collected on the “Adverse Events Details” form on the eCRF and are recorded as the answer (“Yes” or “No”) to “Is this adverse event a dose limiting toxicity?” A DLT is defined as a toxicity of interest judged to be related to avelumab by the investigator and/or the SMC using the National Cancer Institute – Common Terminology Criteria for Adverse Events (NCI-CTCAE) version 4.03. Per the NCI-CTCAE, a DLT is defined as any of the following toxicities at any dose level and judged to be related to the study drug by the investigator and/or the SMC:

- Grade 4 neutropenia for more than 7 days
- Grade ≥ 3 febrile neutropenic infection
- Grade ≥ 3 thrombocytopenia with bleeding
- Grade 4 thrombocytopenia for more than 7 days
- Grade 4 anemia
- Any Grade ≥ 3 toxicity, except for the following:
 - Transient (≤ 72 hours) grade 3 flu-like symptoms or fever, which is controlled with medical management
 - Transient (≤ 72 hours) grade 3 fatigue, local reactions, headache, nausea, or emesis that resolves to grade ≤ 1 or to baseline
 - Grade 3 diarrhea or Grade 3 skin toxicity that resolves to Grade ≤ 1 in less than 7 days after medical management (eg immunosuppressant treatment) has been initiated

- Grade ≥ 3 amylase or lipase abnormality that is not associated with clinical manifestations of pancreatitis
- Tumor flare phenomenon, defined as local pain, irritation, or rash localized at sites of known or suspected tumor
- Single laboratory values out of normal range that are unlikely related to study drug according to the Investigator, do not have any clinical correlate, and resolve to Grade ≤ 1 or Baseline within 7 days with adequate medical management
- Inability to complete at least 2 infusions of avelumab during the DLT observation period due to treatment-related toxicity

While the rules for adjudicating DLTs are specified above, an AE not listed above, or an AE meeting the DLT criteria above but occurring outside of the DLT observation period, may be defined as a DLT after consultation between Sponsor and Investigator, based on the emerging safety profile. DLTs may be identified by the site investigator or by the SMC. Analyses of DLTs will be conducted as per the SMC assessment.

The DLT summary table will present the following for the DLT analysis set:

- the number and percentage of subjects who experienced a DLT during the DLT evaluation period with corresponding two-sided exact Clopper-Pearson (3) 95% confidence intervals (CIs)
- the number and percentage of subjects who experienced a TEAE during the DLT evaluation period with corresponding two-sided exact Clopper-Pearson (3) 95% CIs
- the number and percentage of subjects who experienced a TEAE grade ≥ 3 during the DLT evaluation period with corresponding two-sided exact Clopper-Pearson (3) 95% CIs
- DLTs during the DLT evaluation period by SOC and PT

There will be no imputation of missing data for the DLT variable. A flag on the Adverse Events listing will indicate if a given AE was determined to be a DLT, per the SMC.

The maximum tolerated dose (MTD) is defined as the highest dose tested of avelumab associated with the occurrence of DLTs within the DLT evaluation period in $<33\%$ of subjects, provided that a higher dose of avelumab was tested and had an associated DLT rate $\geq 33\%$. If the DLT rate within the DLT evaluation period is $< 33\%$ for all tested dose levels, then the MTD will not have been reached. If the starting dose level is confirmed as safe, this dose will be selected as the RP2D if it provides similar exposure in children to those in adults. If exposure is not adequate, a decision can be made to escalate to a dose level up to 20 mg/kg.

Dose escalation/de-escalation rules will follow the modified toxicity probability interval (mTPI) method described in Section 5.1.1.1.1 of the CTP. The mTPI method relies on a statistical probability algorithm to compute the posterior probability of 3 dosing intervals that reflect the relative difference between the toxicity rate of each dose level to the target probability rate ($pT =$

0.3), using all subjects treated in prior and current cohorts at the same dose level to determine whether future cohorts should involve dose re-escalation, no change in dose, or dose de-escalation. The detailed dose-finding rules based on the mTPI are illustrated below in Table 5.

Table 5 Detailed Dose Re-Escalation/De-Escalation Scheme

		Number of Subjects Treated at Current Dose											
		1	2	3	4	5	6	7	8	9	10	11	12
Number of DLTs	0	NA	NA	E	E	E	E	E	E	E	E	E	E
	1	D	S	S	S	S	E	E	E	E	E	E	E
	2		DU	D	S	S	S	S	S	S	S	S	E
	3			DU	DU	D	D	S	S	S	S	S	S
	4				DU	DU	DU	D	D	S	S	S	S
	5					DU	DU	DU	DU	DU	D	S	S
	6						DU	DU	DU	DU	DU	DU	D
	7							DU	DU	DU	DU	DU	DU
	8								DU	DU	DU	DU	DU
	9									DU	DU	DU	DU
	10										DU	DU	DU
	11											DU	DU
	12												DU

E = Escalate to the next higher dose, or if current dose level is DL1, stay on DL1. Escalation to DL2 is allowed if exposure at DL 1 is not adequate.
 S = Stay at the current dose.
 D = De-escalate to the next lower dose level.
 DU = De-escalate to the next lower dose level; the current dose is unacceptably toxic.
 Targeted DLT rate at MTD = 33%.

